Study Design	
 This is a Phase II, randomised, double-blind, parallel group, placebo-controlled, multicentre study of 52 weeks treatment duration in subjects with NOT1DM. Approximately 68 eligible subjects will be randomised in a 3:1 ratio such that 51 subjects receive albiglutide 30 mg once weekly (with blinded increase to 50 mg once weekly at Week 6 if the 30 mg dose is tolerated) added-on to insulin therapy and 17 subjects receive placebo once weekly added-on to insulin therapy. Historical data from placebo patients, aged 18-30 from the DEFEND-1 study [GlaxoSmithKline Document Number, 2011N125757_00] will be incorporated into the primary endpoint analysis, using Bayesian analysis. Blinded reduction of randomised study medication to the 30 mg once weekly dose may occur in the event of GI intolerance (i.e., nausea, vomiting or diarrhoea) after discussion between the investigator and medical monitor. During the study, subjects will perform self-monitored plasma glucose monitoring at least 4 times daily and adjust their basal and meal-time insulin requirements according to protocol-defined algorithm/guidance. A sample size of 60 evaluable subjects (45 in the albiglutide group and 15 in the placebo group) provides 90% power to detect a treatment effect in the primary endpoint of the current study in the range of 0.19 nmol/L (using data from all 53 placebo subjects aged 18-30 from the DEFEND-1 study) to 0.30 nmol/L (not using any historical data). The corresponding minimal detectable difference will be 0.12 nmol/L to 0.18 nmol/L, respectively. The total duration of a subject's participation will be approximately 72 weeks (up to 8 weeks of Screening, 52 weeks of treatment and 12 weeks of Post-treatment Follow-up).
Planned Analyses	
 No interim analysis is planned for this study. All decisions regarding final analysis, as defined in this RAP document, will be made prior to unblinding of the study data.

Overview	Key Elements of the RAP
Analysis Populations	
 The 'Intent to Treat' Population will be used to evaluate study efficacy. The 'Safety' Population will be used to evaluate study population characteristics, safety and PD/Biomarkers, and the 'PK' Population to evaluate pharmacokinetics.

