
 'In analyses of HbA1c and insulin usage, missing data at key analysis time points will be imputed using the last observation carried forward method.' 	
 The imputation of missing data using the last observation carried forward method will not be done for HbA1c or insulin usage. No imputation of missing data. The MMRM methodology will be used for statistical analysis. 	
 Feedback from the FDA for a different albiglutide study indicated that the LOCF approach was no longer acceptable.

 The protocol states 'Laboratory values below the level of quantification (BLQ) will be set to one-half the limit of quantification (unless noted otherwise) in computations for the aggregate analyses, but will be noted as BLQ in the listings' 	
 Laboratory results that are beyond the limits of quantification will have the inequality sign dropped (<, ≤, >, or ≥) and the quantification limit will be used as the numeric result for summarisation. 	
 To be consistent with how these values are handled in other albiglutide studies.

 The protocol specified that 'age group' would fitted as an independent variable in the mixed effects model 	
 Age (years) will be fitted as a continuous covariate where the statistical models allow. 	
 To better allow for the effect of age which could not be easily categorised into meaningful groups

 In the mixed effect model specification baseline-by-visit interaction was not included as a term in the model. 	
 'Inclusion of the term baseline-by-visit may be considered in the final model based on model fit and/or convergence.' 	
 In order to allow differences in treatment response according to baseline value; however due to the small sample size in this study there may be convergence problems when including this additional term.

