
 Least squares means and corresponding standard error of means (SEs) for change from baseline will be presented for each treatment group at each time-point. The estimated treatment difference, associated 95% confidence interval and p-value will be presented at each time-point. 	

Secondary Statistical Analyses	
Summary TFLs	

 Summary statistics for absolute and change from baseline will be presented for each treatment group at all visits (including visits with no statistical analysis performed) For C-peptide AUC, plots of mean absolute (\pm SE) and mean change from baseline (\pm SE) will be presented for each treatment group over time For other endpoints, plots of mean absolute (\pm SE) will be presented for each treatment group over time Data will be listed. 	
HbA1c	

 Statistical analysis of HbA1c will be performed using HbA1c in units of %. Summary statistics for absolute and change from baseline will be presented in units of % and in units of mmol/mol Plots will be presented using units of % Data listings will contain both units of % and units of mmol/mol 	
Endpoint(s)	

 Percentage of Responders (defined as subjects with HbA1c \leq 7.0 and mean daily insulin use <0.5 units/kg/day) at Week 28 and 52 Percentage of subjects achieving partial remission status (i.e., insulin dose-adjusted haemoglobin A1c [IDAA1C] \leq 9.0) at Week 28 and 52 	
Model Specification	

 The treatment comparison will be undertaken with a non-parametric, covariance-adjusted, extended Mantel-Haenszel test using the SAS FREQ procedure. Age (categorical) will be included as a covariate. This technique is especially suited for situations in which covariance adjustment is needed to optimise statistical power, while minimizing the modeling assumptions. 	
Model Checking & Diagnostics	

 Not applicable 	
Model Results Presentation	

 The odds ratio, associated 95% confidence interval and p-value for the treatment difference will be presented at each time-point. 	
Additional Covariate Information	

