
 In this analysis, age will be included as a categorical covariate. Age will be dichotomised into a binary variable, based on whether a subject's age is above or below the median age (overall subjects in the ITT population). Age categories: $<$ median age (years); \geq median age (years) 	
Missing data	

 In a change from the planned analysis, the LOCF method will not be used for HbA1c and insulin usage. All available data will be used for the analysis. A post-hoc sensitivity analysis imputing missing data may be performed if needed, but is not currently planned to be performed. If a subject has missing HbA1c/insulin use data and the reason why the value is missing is not related to efficacy or safety (e.g., procedural) and could be assumed that the value is missing at random, then the value would be left as missing for calculations; if the reason why the value is missing is lack of efficacy or due to safety, then this missing value would be imputed as 'not meeting target' and included in the denominator in the calculations of the proportion of responders. See Section 11.6.2.2 for further details. 	

Secondary Statistical Analyses
Summary TFLs

Responders/Partial Remission:
 
 • The proportion of responders (number and percentage) will be presented for each treatment group at all visits (including visits with no statistical analysis performed). • The proportion of responders over time will be presented graphically for each treatment group. • Data will be listed.
Endpoint(s)

 • Number of events of hypoglycaemia with confirmed self plasma glucose monitoring ≤ 3.9 mmol/L and/or requiring third party intervention (i.e. severe, documented symptomatic and asymptomatic hypoglycaemic events) occurring $>$Week 24 and \leqWeek 52. • Number and magnitude of hypoglycaemic (≤ 3.9 mmol/L) excursions from the 7-point glucose profile at Baseline, Week 28 and Week 52 • Number and magnitude of hyperglycaemic (>10.0 mmol/L) excursions from the 7-point glucose profile at Baseline, Week 28 and Week 52
Model Specification

 • Formal comparative statistical analysis will not be performed for these endpoints.
Model Checking & Diagnostics

 • Not applicable.
Model Results Presentation

 • Not applicable.
Summary TFLs

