11.6.2.2. Handling of Missing Data for Statistical Analysis

Element	Reporting Detail
LOCF	
 With LOCF, missing values would be carried forward from the previous, non-missing available on-treatment assessment. The protocol specified that 'In analyses of HbA1c and insulin usage, missing data at key analysis time points will be imputed using the last observation carried forward method.' In a change to the planned analysis, the last observation carried forward method will not be used for HbA1c and insulin usage. Therefore the LOCF method is not used in this study for any endpoints or analyses.
Responder analysis and Partial Remission Status analysis	
 A post-hoc sensitivity analysis imputing missing data may be performed if needed, but is not currently planned to be performed. If a subject has missing HbA1c/insulin use data and the reason why the value is missing is not related to efficacy or safety (e.g., procedural) and could be assumed that the value is missing at random, then the value would be left as missing for calculations; if the reason why the value is missing is lack of efficacy or due to safety, then this missing value would be imputed as 'not meeting target' and included in the denominator in the calculations of the proportion of responders. Reasons for study withdrawal of adverse event (excluding pregnancy) would be considered as potentially missing due to lack of efficacy or safety. Reasons for study withdrawal of lost to follow, investigator discretion or withdrew consent would be reviewed and further information from sites investigated, to determine if these should be considered as potentially missing due to lack of efficacy or safety. Reasons for study withdrawal of pregnancy, protocol deviation, study closed/terminated or investigator site closed would be considered as missing at random
MMRM analyses	
 Missing data are not explicitly imputed in MMRM analyses; although there is an underlying assumption that data are missing at random, including those withdrawn for lack of efficacy. The MMRM method will produce an unbiased estimate of treatment effect under the missing at random (MAR) assumption. Under a MAR assumption where the missing data may depend on the prior observations, i.e., the conditional independence assumption, the model provides unbiased LSmean estimates for the treatment groups at the assessment time points

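### The responder and partial-remission tests adjust for median-split age but not for baseline, and the SAP's own rule for counting withdrawals as failures is left as an optional post-hoc analysis

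*SAP*

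**What the plan says.** **Covariates.** SAP Section 8.1.2 compares the arms on both binary endpoints with a covariance-adjusted extended Mantel-Haenszel test in PROC FREQ. It justifies the choice thus: "This technique is especially suited for situations in which covariance adjustment is needed to optimise statistical power, while minimizing the modeling assumptions". One covariate follows: "Age (categorical) will be included as a covariate", split at the ITT median. Protocol Section 8.3.5.3.2 names the same test and no covariates. SAP Section 11.8.1 lists only age and adds that other covariates might be considered, without naming any or fixing a time for the choice. The secondary MMRMs in Section 8.1.2, including those for HbA1c and daily insulin, fit baseline and continuous age. Protocol Section 6.1 lists HbA1c and insulin usage among the critical baseline assessments.

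**Missing data.** The protocol's LOCF for HbA1c and insulin is dropped in SAP Table 1: "No imputation of missing data. The MMRM methodology will be used for statistical analysis". For the binary endpoints, Section 8.1.2 says "All available data will be used for the analysis". It then describes a rule that counts a value missing for safety or lack of efficacy as not meeting the target and leaves procedural gaps missing. The status of that rule is "A post-hoc sensitivity analysis imputing missing data may be performed if needed, but is not currently planned to be performed". Section 11.6.2.2 gives the mapping: "Reasons for study withdrawal of adverse event (excluding pregnancy) would be considered as potentially missing due to lack of efficacy or safety", while "Reasons for study withdrawal of lost to follow, investigator discretion or withdrew consent would be reviewed and further information from sites investigated". The Synopsis states "All decisions regarding final analysis, as defined in this RAP document, will be made prior to unblinding of the study data".

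**The concern.** The test was chosen for its ability to use covariates, yet the covariates most likely to predict whether a subject later meets an HbA1c and insulin threshold are not named. With about 15 placebo subjects, this gives up precision and protection against chance imbalance.

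The MMRM that replaces LOCF does not analyse these binary endpoints, so they have no planned missing-data sensitivity analysis at all. The rule that would fill the gap has no trigger beyond need, and nothing says that the ambiguous withdrawals are sorted while blinded. Both the decision to run it and the classification could therefore be made with results in view.

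**Working it through.** **The plan's own figures.** The documents give no response rates, effect size or power for these endpoints, so there is no stated figure to reproduce. Protocol Section 8.2.1 gives 68 randomised (51 and 17), 10% drop-out and 60 evaluable (45 and 15): 68 × 0.90 = 61.2, taken as 60. That leaves 51 − 45 = 6 and 17 − 15 = 2 subjects missing.

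**1. Missing data (response rates assumed).** Responders are fixed at a and b. If k1 of the 6 and k2 of the 2 missing subjects count as failures, the difference is a/(45+k1) − b/(15+k2). The p-value is from the unstratified Mantel-Haenszel chi-square without continuity correction.

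| k1, k2 | 24 vs 4 responders | 36 vs 8 responders |
|---|---|---|
| 0, 0 (available cases) | 53.3 − 26.7 = 26.7, p=0.075 | 80.0 − 53.3 = 26.7, p=0.045 |
| 3, 1 (proportional) | 50.0 − 25.0 = 25.0, p=0.083 | 75.0 − 50.0 = 25.0, p=0.064 |
| 6, 2 (proportional) | 47.1 − 23.5 = 23.5, p=0.090 | 70.6 − 47.1 = 23.5, p=0.081 |
| 6, 0 (albiglutide only) | 47.1 − 26.7 = 20.4, p=0.163 | 70.6 − 53.3 = 17.3, p=0.216 |
| 0, 2 (placebo only) | 53.3 − 23.5 = 29.8, p=0.037 | 80.0 − 47.1 = 32.9, p=0.011 |

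Proportional withdrawals move the difference by 26.7 − 25.0 = 1.7 to 26.7 − 23.5 = 3.2 points. One-sided withdrawals move it by at most 26.7 − 20.4 = 6.3 points in the first column and 26.7 − 17.3 = 9.4 in the second. With 18/45 versus 3/15 the difference is 20.0, with a range of 15.3 to 22.4.

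These are upper bounds:
- The table restores all 51 and 17 randomised. The tests use the ITT population (SAP Section 4), which needs a post-baseline assessment of the primary endpoint, first scheduled at Week 16. Earlier leavers cannot be counted.
- The extremes need every missing subject in one arm, and none in the other, to be classed as a failure.
- Responder status is also lost when an insulin component is unevaluable (SAP Section 11.5.4). Where that is procedural, the rule leaves it missing.

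**2. Covariates (simulation, correlations and rates assumed).** There were 10,000 trials per setting with 45 versus 15 subjects, age uniform on 18 to 30, and response defined as a latent normal variable above a cut. Placebo response was 25, 35 or 50%, and the latent treatment shift 0.8. The planned test is Mantel-Haenszel stratified by age below, or at and above, the median. The alternative regresses response on baseline and continuous age with arms pooled, then refers (N−1)r² between residual and treatment to chi-square with 1 df. Power of the planned test is 52 to 57%.

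| Correlation of baseline with outcome | Change in power, points (placebo 25 / 35 / 50%) |
|---|---|
| 0 | −0.3 / −0.5 / −0.5 |
| 0.2 | +0.8 / +0.3 / +0.3 |
| 0.4 | +3.3 / +3.8 / +3.4 |
| 0.6 | +10.6 / +10.1 / +8.4 |

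A separate rerun agreed within simulation error, giving −0.9 to −0.7 at correlation 0 and +7.9 to +10.9 at 0.6. With no treatment effect, both tests reject in about 4.5 to 5.3% of trials. With 20% of baseline values missing and filled with the pooled mean, the gains are +2.4 to +3.0 at 0.4 and +6.4 to +7.7 at 0.6.

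**The case against.** The choice of covariate is largely a preference. The protocol names none, the SAP fixes one, and the gain is material only at correlations that the documents do not supply. The MMRMs model change from baseline, whereas these endpoints are absolute thresholds, so the parallel is imperfect. SAP Table 1 reports data collection problems with daily insulin, the variable one would adjust for. It also says why analyses are few: a small study, and a product not being developed for this indication. The failure rule is written out in detail, openly labelled post hoc, and belongs only to the optional analysis.

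Most of this stands, and it sets the weight of the point. It also makes baseline HbA1c a safer covariate than baseline insulin. It does not explain why an already written rule should wait for an undefined need.

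Stronger readings are tempting, and the documents do not support them:
- *The tests are biased or invalid without baseline.* They are not: the comparison is randomised and the null rejection rate is unaffected.
- *The SAP contradicts itself by not applying its own rule.* It never presents the rule as the main analysis.
- *Baseline adjustment is ruled out.* Section 11.8.1 leaves it open.
- *Withdrawals will be classified unblinded.* The SAP is silent on this, and the Synopsis places decisions on the final analysis before unblinding. Whether that protects an analysis labelled post hoc is unclear.
- *Withdrawal from study drug creates the missing data.* Protocol Section 4.4 asks these subjects to keep attending the MMTT visits, with HbA1c and insulin use assessed.

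**Conclusion.** Both parts hold, and the point is minor. Omitting baseline costs about nothing if its correlation with outcome is 0 to 0.2, about 3 to 4 points of power at 0.4 and 8 to 10 at 0.6. The failure rule shifts the difference by about 2 to 3 points under proportional withdrawal, and by at most about 6 points (24/45 vs 4/15) or 9 points (36/45 vs 8/15) if withdrawals are one-sided. Near the 5% line even a proportional shift can change the test result: 36/45 versus 8/15 goes from p=0.045 to 0.064 or 0.081. All response rates, correlations and missingness patterns are assumptions. Only two secondary endpoints, with no multiplicity control (SAP Section 5), are affected.

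**What to change.** Before unblinding:

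(a) Keep the named test and add baseline HbA1c and continuous age as covariates, for example as a mean-score test on regression residuals in PROC FREQ. Add baseline insulin use or IDAA1c where evaluable, filling gaps with the blinded pooled mean so that no subject drops out. Keep the planned age-stratified odds ratio and interval, labelled as adjusted for age only, and note that they can disagree with the adjusted p-value. In the simulation they disagree on significance in about 11 to 14% of trials at correlation 0.4 and 16 to 22% at 0.6. That mismatch comes from this proposal, not from the SAP. A model-based odds ratio would reduce it, but adds modelling assumptions that the SAP sets out to minimise, so it is not requested.

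(b) Keep available cases as the main analysis. Make the Section 11.6.2.2 failure rule a planned sensitivity analysis in the ITT population at Weeks 28 and 52. State that lost to follow-up, investigator discretion and withdrew consent are classified while blinded.

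The cost is SAP wording, a blinded review of a few withdrawals, one extra table per endpoint, a little programming, and up to about 1 point of power if baseline is not prognostic.

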8.2. Safety Analyses

8.2.1. Overview of Planned Adverse Events Analyses

The safety analyses will be based on the “Safety” population, unless otherwise specified.

Table 6 provides an overview of the planned analyses, with further details of data displays being presented in [Appendix 13: List of Data Displays](#).

Table 6 Overview of Planned Adverse Event Analyses

Endpoint / Parameter/ Display Type	Absolute		
	Summary		Individual
	T	F	L
Adverse Events (AEs)			
Overview of AEs	Y		
All AEs by SOC and PT	Y [2]		Y
Common AEs by Overall Frequency	Y [3]		
Drug-Related AEs by SOC and PT	Y [2]		
All AEs by SOC and PT and Maximum Intensity	Y [2]		
Drug-Related AEs by SOC and PT and Maximum Intensity	Y [2]		
Common Non-Serious AEs by SOC and PT (Subjects & No. of Occurrences)	Y [3]		
Subject Numbers for Individual AEs			Y
Relationship Between AE SOCs, PT and Verbatim Text			Y
Serious and Other Significant AEs			
Serious AEs	Y [1]		
Reasons for Considering as a Serious AE			Y
Drug-Related Serious AEs [9]			
Serious AEs by SOC and PT (Subjects & No. of Occurrences)	Y [3]		
Fatal Serious AEs [9]			Y
Drug-Related Fatal Serious AEs [9]			
Non-Fatal Serious AEs [9]			Y
Drug-Related Non-Fatal Fatal Serious AEs [9]			
AEs Leading to Permanent Discontinuation of Study Treatment by SOC and PT	Y [3]		Y
AEs Leading to Withdrawal from Study by SOC and PT	Y [2]		Y
Other Significant AEs [7]			
AEs of Special Interest			
Overview of Adverse Events of Special Interest	Y [3]		
Investigator-Reported Cardiovascular Events by SOC and PT	Y [3]		Y
Investigator-Reported Atrial Fibrillation/Atrial Flutter by SOC and PT	Y [3]		Y
Subject-Reported Hypoglycaemic Events by ADA category in 3-monthly Intervals	Y [6]		
Subject-Reported Hypoglycaemic Events with plasma glucose <3.1 mmol/L	Y [6]		
Subject-Reported Daytime/Nocturnal Hypoglycaemic Events by ADA category	Y [6]		
Subject-Reported Hypoglycaemic Events over Time	Y [6]	Y [6]	
Subject-Reported Hypoglycaemic Events			Y
Investigator-Reported Pneumonia Events by SOC and PT	Y [3]		Y
Investigator-Reported Pancreatitis Events by SOC and PT	Y [3]		Y

Endpoint / Parameter/ Display Type	Absolute		
	Summary		Individual
	T	F	L
Positively Adjudicated Pancreatitis Events by SOC and PT	Y [3]		
Investigator-Reported Thyroid Adverse Events by SOC and PT	Y [3]		Y
Gastrointestinal (GI) Events by SOC and PT	Y [3]		
GI Events Over Time [4]	Y [3]		
Summary of Characteristics of Events [5]	Y [3]		
Investigator-Reported Investigational Product Injection Site Reactions by SOC and PT	Y [3]		Y
Summary Characteristics of Investigator-Reported Investigational Product Injection Site Reactions	Y [3]		
Summary Characteristics of Investigator-Reported Investigational Product Injection Site Reactions by Anti-Albiglutide Antibody Status	Y [3]		
Investigator-Reported Systemic Allergic Reactions	Y [3]		Y
Liver Monitoring/Stopping Event Reporting	Y [8]		Y
Liver Events (Customised MedDRA Query) by SOC and PT	Y [3]		Y
Investigator-Reported Renal Impairment by SOC and PT	Y [3]		Y
Diabetic Ketoacidosis (DKA) by SOC and PT	Y [3]		Y
Appendicitis by SOC and PT	Y [3]		Y
Pancreatic Cancer by SOC and PT	Y [3]		Y
Malignant Neoplasms by SOC and PT	Y [3]		Y

NOTES:

- T = Table, F = Figures, L = Listings, Y = Yes display generated, SOC = System Organ Class, PT = Preferred Term.
- Summary = Represents TF related to any summaries (i.e. descriptive statistics) of the observed raw data.
- Individual = Represents FL related to any displays of individual subject observed raw data.
- [1] Produced for the pre-therapy, on-therapy and post-therapy phases separately.
- [2] Produced for the on-therapy and post-therapy phases separately.
- [3] Produced for the on-therapy phase only.
- [4] Produced for any GI event
- [5] Produced for Diarrhoea, Nausea, and Vomiting
- [6] Includes all events, on-therapy and post-therapy combined.
- [7] There are no other significant adverse events identified in this study; however AEs of special interest have been defined.
- [8] Combined on-therapy and post-therapy summary table.
- [9] Due to the low number of serious AEs reported, summary tables will not be produced for these events.

